4.8 OTHER ANALYSES

4.8.1 PK analyses

Predose serum dupilumab concentrations at Visit 2 (Day 1), dupilumab trough levels at Week 12, Week 24/EOT and posttreatment serum dupilumab at Week 36 will be provided.

Serum concentrations of SAR231893 (REGN668) will be summarized in the PK population using arithmetic and geometric means, SD, standard error of the mean (SEM), coefficient of variation (CV), minimum, median and maximum per sampling time. If date and/or time of the drug injection and/or sampling is missing, then the concentration will not be taken into account. For drug-treated participants, where concentration values are below the lower limit of quantification (LLOQ), the baseline concentration will be considered equal to 0, and one-half of the LLOQ will be used for post-baseline concentrations. Values will be expressed in the tables with no more than three significant figures. For participants in the placebo group, concentration values are below the LLOQ will be taken into account with a plasma concentration considered equal to 0.

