- If the participant misses more than 2 consecutive doses of the IMP (see [Section 7.1.2](#)).
- Systemic hypersensitivity reaction including anaphylaxis related or suspected to be related to ice cube provocation test. In the participants who experienced such reaction no further ice cube provocation test should be done during the study.

See the SoA ([Section 1.3](#)) for data to be collected at the time of intervention discontinuation and follow-up and for any further evaluations that need to be completed.

Any abnormal laboratory value or ECG parameter will be immediately rechecked for confirmation within a reasonable timeframe as assessed by the Investigator before making a decision of definitive discontinuation of the IMP for the concerned participant.

If a clinically significant ECG finding is identified (including, but not limited to changes from baseline in QT interval corrected using [Bazett's formula {QTcB} or Fridericia's formula {QTcF}]) at screening, the Investigator or qualified designee will determine if the participant is eligible for the study. This review of the ECG printed at the time of collection must be documented. Any new clinically relevant finding should be reported as an AE.

Handling of participants after definitive intervention discontinuation

Participants will be followed-up according to the study procedures specified in this protocol up to the scheduled date of study completion, or up to recovery or stabilization of any AE to be followed-up as specified in this protocol, whichever comes last.

Participants who discontinue the study intervention prematurely (prior to completing the 24-week treatment period) will perform, as soon as possible, the early treatment discontinuation Visit with all assessments normally planned for the EOT visit (Visit 4), to assure a complete clinical assessment in close temporal proximity to the premature termination of study treatment is available.

In addition, and to allow assessment of participant outcomes over the stipulated study period, participants will be asked and encouraged to complete all remaining study treatment visits and participate in safety follow-up according to the visit schedule with a ± 3 day window. Under exceptional circumstances when a participant cannot come to the study center for a scheduled visit, a phone contact can be made. During the phone contact, at least information about AEs, concomitant medication and status of urticaria should be collected.

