8.4 TREATMENT OF OVERDOSE

Symptomatic overdose (serious or nonserious) with IMP/NIMP is considered as an AESI (defined in [Section 8.3.7](#)). No antidote is available for dupilumab. The Sponsor does not recommend specific treatment for an overdose.

In the event of an overdose, the Investigator/treating physician should:

1. Contact the Sponsor immediately.
2. Closely monitor the participant for any AE/SAE and laboratory abnormalities until dupilumab can no longer be detected systemically (at least 98 days).
3. Obtain a plasma sample for PK analysis as soon as possible from the date of the last dose of IMP if requested by the Sponsor (determined on a case-by-case basis).
4. Document appropriately in the eCRF.

Decisions regarding dose interruptions will be made by the Investigator in consultation with the Sponsor based on the clinical evaluation of the participant.

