3 ANALYSIS POPULATIONS

The following populations for analyses are defined:

Table 3 - Populations for analyses

Population	Description
Screened	All participants who sign the ICF
Randomized	All participants from the screened population who have been allocated to a randomized intervention by IRT regardless of whether the treatment kit was used or not. Participants treated without being randomized will not be considered randomized and will not be included in any efficacy population.
Intent-to-treat (ITT)	All randomized participants analyzed according to the intervention group allocated by randomization.
Safety	All participants randomly assigned to study intervention and who take at least 1 dose of study intervention. Participants will be analyzed according to the intervention they actually received. Randomized participants for whom it is unclear whether they took the study medication will be included in the safety population as randomized. For participants who accidentally receive a different intervention from that which was planned, the actual intervention allocation for as-treated analysis will be the dupilumab group. The pharmacodynamic (PD) analyses will be performed on the safety population.
Pharmacokinetic (PK)	The PK population includes all participants in the safety population with at least one non-missing result for functional dupilumab concentration in serum after first dose of the study intervention. Participants will be analyzed according to the intervention actually received.
Anti-drug antibody (ADA)	ADA population includes all participants in the safety population who have at least one non-missing ADA result after first dose of the study intervention. Participants will be analyzed according to the intervention actually received.

Abbreviations: ITT = intent-to-treat, ADA = antidirug antibody; ICF = Informed consent form, IRT = Interactive response technology; PD = Pharmacodynamic, PK = Pharmacokinetic

Participants exposed to study intervention before or without being randomized will not be considered randomized and will not be included in any analysis population. The safety experience of these participants will be reported separately.

Randomized participants for whom it is unclear whether they took the study intervention will be considered as exposed and will be included in the safety population as randomized.

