4.8.2.1 Association of Immunogenicity with Exposure, Safety and Efficacy

The safety and efficacy analysis mentioned below will be conducted using the following categories:

ADA positive participants: Participants with treatment-emergent or treatment-boosted response.

ADA negative participants: Participants with pre-existing immunoreactivity or negative in the ADA assay at all time points.

Impact of ADA on PK profile

Potential associations between ADA variables (e.g., ADA peak titers, neutralizing antibody status, treatment-emergent, persistent, indeterminate and transient response, treatment-boosted) and impact on serum concentration profile of dupilumab may be explored. Plot of serum concentration of functional dupilumab versus visit will be provided by ADA variables for dupilumab group. Individual participant plots of dupilumab concentration according to ADA status will be provided.

Impact of ADA on clinical efficacy endpoints

Associations between the ADA variables (e.g., ADA peak titers, neutralizing antibody status, treatment-emergent, persistent, treatment-boosted) and the primary efficacy endpoint may be explored for the dupilumab dosed group.

Association of ADA with clinical safety endpoints

Association of safety versus ADA status may be analyzed in the ADA population. The safety assessment may focus on the following events:

- Severe injection site reactions last longer than 24 hours or serious injection site reactions
- Hypersensitivity reactions (SMQ (20000214) hypersensitivity narrow search confirmed by medical review)
- Anaphylactic reactions (SMQ (20000021) anaphylactic reaction narrow search)

Associations between ADA variables (e.g., ADA peak titers, neutralizing antibody status, treatment-emergent, persistent and treatment-boosted) and safety may be explored.

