For the efficacy assessment, the reference date for the derivation of relative days of events or findings will be the randomization day. If a participant receives IMP prior to the randomization by mistake, the reference date of efficacy assessment will be the date of the first IMP administration for that participant. For the primary analyses, all available values of scheduled measurements will be assigned to the appropriate visit window according to [Table 10](#). In the event of multiple measurements of the same test in the same window, the one closest to the targeted visit date will be used for the by-visit summary. If they are at the same number of days away from the target day, the latest one will be used.

Table 10 - Time window for efficacy variables

Visit	Target Day	Time windows for				
		Ice cube, UCT	Likert, NRS	ColdUAS, PGIS	PGIC	DLQI/CDLQI, ColdU-QoL, EQ-5D-5L, [REDACTED]
Visit 1	-28 to -14	<-14		<-14		
Visit 2 (Week 0)	1	-14-1-	<1-	-14-1-		<1-
Visit 3 (Week 12)	85	1+-126	1+-126	1+-126	1+-126	
Visit 4 (Week 24)	169	127-210	127-210	>126	>126	≥1+
Visit 5 (Week 36)	253	>210	>210			

1-: up to randomization and before 1st dose date/time; 1+: after randomization or 1st dose date/time

For the pharmacokinetics/pharmacodynamics variables summary, the reference date for the derivation of relative days of measurements will be the date of first IMP administration if the participant is treated with study intervention, or the randomization date if the participant is not treated. Pharmacokinetics/pharmacodynamics variables will be summarized by the analysis window defined in [Table 11](#) for the by visit descriptive analyses. All available values of measurements will be assigned to the appropriate visit window. In the event of multiple measurements of the same test in the same window, the one closest to the targeted visit date will be used for the by-visit summary. If they are at the same number of days away from the target day, the latest one will be used. For procedures planned on Visit 2, if it is done on the same date as the first IMP injection but the performance time is missing, it will belong to Visit 2 time window.

Table 11 - Time window for pharmacokinetics/pharmacodynamics variables

Visit	Target Day	Serum dupilumab, ADA, Total IgE	Basophil activation (optional)
Visit 1	-28 to -14		
Visit 2 (Week 0)	1	<1-	<1-
Visit 3 (Week 12)	85	1+-126	1+-126
Visit 4 (Week 24)	169	127-210	>126
Visit 5 (Week 36)	253	>210	

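### SAP 4.8.1 reports Week 12 and Week 24 trough concentrations, but samples are assigned by days from first dose with no limit on time since the last dose, so off-drug and late samples are counted as troughs

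*SAP*

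**What the plan says.** SAP 4.8.1 names the quantities to be reported: "dupilumab trough levels at Week 12, Week 24/EOT and posttreatment serum dupilumab at Week 36 will be provided". They are summarised in the PK population by arithmetic and geometric mean, SD, SEM, CV, minimum, median and maximum. A sample is dropped only if the date or time of injection or sampling is missing. In drug-treated participants a post-baseline value below the LLOQ is replaced by half the LLOQ.

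SAP Section 3 sets the population: "The PK population includes all participants in the safety population with at least one non-missing result for functional dupilumab concentration" after the first dose. It has no on-treatment condition.

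SAP 5.4 (Appendix 4) sets the timing. For treated participants "the reference date for the derivation of relative days of measurements will be the date of first IMP administration". Then: "All available values of measurements will be assigned to the appropriate visit window". Table 11 gives Week 12 as after the first dose to Day 126 (target Day 85), Week 24 as Days 127 to 210 (target Day 169), and Week 36 as after Day 210. With several samples in one window, "the one closest to the targeted visit date will be used for the by-visit summary".

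Protocol 7.1.1 asks those who stop IMP to have an early visit with all the end-of-treatment assessments, and beyond that "participants will be asked and encouraged to complete all remaining study treatment visits". The Schedule of Activities has PK sampling at Weeks 12, 24 and 36.

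SAP 4.8.2.1 uses the same concentrations again: "Plot of serum concentration of functional dupilumab versus visit will be provided by ADA variables for dupilumab group".

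**The concern.** A trough is the concentration at the end of a dosing interval, just before the next dose. That needs a clock starting at the most recent dose. The SAP's clock starts at the first dose, so whether a value is a trough depends on dosing having continued on schedule, and nothing checks that it did.

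Three kinds of sample can be mislabelled: those from participants who stopped IMP but still attend, those taken after missed doses, and those taken late within a wide window. All three tend to read low. The trough table is this trial's description of exposure in cold urticaria. In the ADA plots, a low value caused by stopping treatment could be read as an effect of antibodies on exposure, or could hide one.

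The SAP already has the missing idea. Section 4.1 defines an on-treatment period (last IMP dose plus 14 days), and Section 4.7.3.1 applies it to the last and worst laboratory values. The trough rows have no equivalent.

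**Working it through.** The plan states no figure for this point, so there is none to reproduce. The check is day arithmetic on the stated windows, then an illustration of size.

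**Inputs from the documents.** Dosing every 14 ± 3 days, last planned dose at Week 22, which is Day 1 + 22 × 7 = Day 155 (Protocol 6.1.1). Visits at Weeks 12 and 24 ± 3 days (Schedule of Activities). Targets Day 85 and Day 169 (SAP Table 11). Treatment is stopped for good only after more than 2 consecutive missed doses (Protocol 7.1.2). There are two statements on washout: Protocol 8.4 asks for monitoring after an overdose "until dupilumab can no longer be detected systemically (at least 98 days", and Protocol 4.2 bases the 12-week follow-up on the time for drug to fall below quantification in most participants.

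**Step 1: on-schedule participants.** Week 12: 85 − 71 = 14 days since the Week 10 dose. Week 24: 169 − 155 = 14 days. The trough label is right for them.

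**Step 2: participants who stop.** Days since last dose at each target day:

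| Last dose | At Day 85 | At Day 169 |
|---|---|---|
| Day 1 | 84 | 168 |
| Day 29 | 56 | 140 |
| Day 57 | 28 | 112 |
| Day 71 | 14 | 98 |
| Day 85 | – | 84 |
| Day 113 | – | 56 |
| Day 141 | – | 28 |

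A last dose on or before Day 71 (169 − 98) puts the Week 24 sample at least 98 days after dosing. On the 12-week basis the cut-off is Day 85 (169 − 84).

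**Step 3: missed and late samples.** Two missed doses are allowed, so a participant still on treatment can be sampled 3 × 14 = 42 days after dosing. The Week 24 window runs to Day 210, which is 210 − 155 = 55 days after the last planned dose.

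**Step 4: the selection rule.** Suppose the last dose is Day 29, the early-discontinuation sample is Day 40 and the visit sample is Day 85. Distances to target are 45 and 0 days, so Day 85 is chosen, at 56 days off drug.

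**Step 5: illustrative size.** Let *k* of 39 samples sit at half the LLOQ, and let *R* be the on-drug geometric-mean trough divided by half the LLOQ. The geometric mean is multiplied by R^(−k/39). Taking washed-out values as about zero, the arithmetic mean is multiplied by 1 − k/39. Both *k* and *R* are assumptions; the documents show neither the LLOQ nor an expected trough.

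| k | R = 10 | R = 100 | R = 1000 | Arithmetic |
|---|---|---|---|---|
| 1 | 0.94 | 0.89 | 0.84 | 0.97 |
| 2 | 0.89 | 0.79 | 0.70 | 0.95 |
| 4 | 0.79 | 0.62 | 0.49 | 0.90 |

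**Step 6: time since dose within protocol windows.** Taking ± 3 days around the nominal days, a dose on Days 152 to 158 and a visit on Days 166 to 172 give 166 − 158 = 8 to 172 − 152 = 20 days. Week 12 gives the same range: doses on Days 68 to 74, visits on Days 82 to 88.

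**The case against.** For anyone dosed on schedule the label is correct by design, because samples are drawn before dosing and Week 24 falls 14 days after the last planned dose. The summary also includes the median, which a few low values barely move, and the minimum, which would expose them. SAP 4.8.2.1 adds individual concentration plots by ADA status, where washout could be seen. PK is an exploratory, descriptive objective. The ADA comparison is distorted only if stopping differs by ADA status, which nothing in the documents shows. All of this stands, and it limits the consequence. It does not supply the missing rule.

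The illustration is at the upper end. Each counted participant must stop early, still attend Week 24 and be fully washed out. Those stopping later retain some drug and lower the means less. The plan's 10% drop-out figure (about 4 of 39) is no more than a scale for *k*, since people who leave the study give no later sample.

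Event-triggered samples are a secondary matter. The protocol collects them for additional analysis if required or for archiving, and SAP 4.8.1 names only scheduled times. The wording in Appendix 4 leaves it unclear whether they could enter a window. One would replace a scheduled sample only if it were at least as close to the target day, or if the scheduled one were missing.

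**Conclusion.** The concern holds as a minor point. As written, the plan tabulates samples from participants who stopped IMP, missed doses or were sampled late as Week 12 and Week 24 troughs, and carries them into the concentration-by-ADA plots. The descriptive exposure summary is biased downward, mainly in the geometric mean. The amount cannot be determined from the documents, and the factors above depend on the assumed *k* and *R*.

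A reader might infer that everyone whose last dose was before Day 71 is undetectable at Week 24 and therefore enters as half the LLOQ. The documents do not support that. The 98 days in Protocol 8.4 is a minimum monitoring time after an overdose, and Protocol 4.2 speaks of most participants. The supportable statement is that participants last dosed on or before about Day 71 (98 days) or Day 85 (12 weeks) would in most cases be expected at or near the LLOQ at Week 24.

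No efficacy test, estimand or sample size is affected.

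**What to change.** In SAP 4.8.1, define a trough as a scheduled pre-dose sample (or the Week 24 visit sample) at the nominal Week 12 or Week 24 visit, taken within a prespecified time since the last IMP dose. That interval should cover the dosing and visit windows together, for example 8 to 20 days. A limit of 11 to 17 days, the dosing window alone, would discard samples that comply with the protocol. The nominal-visit condition is also needed: without it, the Day 40 early-discontinuation sample in the example, 11 days after a Day 29 dose, could become the Week 12 trough.

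Apply the definition to the Week 12 and Week 24 trough rows and to the concentration-by-ADA plots in SAP 4.8.2.1. Present all other post-dose concentrations (off-treatment, early end-of-treatment, late or event-triggered) separately by days since last dose.

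The cost is a few sentences and one derived variable from dates the SAP already requires. The only downside is a few fewer values in the trough table.

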4.8.2 Immunogenicity analyses

Dupilumab anti-drug antibody (ADA) status (negative or titer value, if positive in the ADA assay) at Visit 2 (Day 1), Week 12, Week 24/EOT and follow up at Week 36 will be provided. The neutralizing antibody status for ADA positive samples will be provided.

Incidence will be provided for the following ADA response categories:

Pre-existing immunoreactivity is defined as:

An ADA positive response in the assay at baseline with all post first dose ADA results negative, OR an ADA positive response at baseline with all post first dose ADA responses less than 4-fold over baseline titer levels.

Treatment-emergent ADA responses are defined as:

A positive response in the ADA assay post first dose, when baseline results are negative or missing.

Treatment-emergent ADA responses are further classified as Persistent, Indeterminate or Transient

- a) Persistent Response- defined as a treatment-emergent ADA response with two or more consecutive ADA positive sampling time points, separated by greater than ($>$) 12-week period (84 days), with no ADA negative samples in between.
- b) Indeterminate Response- defined as a treatment-emergent response with only the last collected sample positive in the ADA assay
- c) Transient Response - defined as a treatment-emergent response that is not considered persistent OR indeterminate

Treatment-boosted response is defined as:

An ADA positive response in the assay post first dose that is greater-than or equal to 4-fold over baseline titer levels, when baseline results are positive.

Titer values (Titer value category)

- Low (Titer <1000)
- Moderate ($1,000 \leq \text{Titer} \leq 10,000$)
- High (Titer $>10,000$)

The following summary will be provided based on ADA population:

- Number (%) of participants with pre-existing immunoreactivity
- Number (%) of participants with treatment-emergent ADA

- The summary statistics (including number, median, Q1, Q3, minimum and maximum) of the peak post-baseline titer for participants with treatment-emergent ADA, and participants with persistent, indeterminate and transient ADA response
- Number (%) of participant with transient treatment-emergent ADA
- Number (%) of participants with persistent treatment-emergent ADA
- Number (%) of participants with indeterminate treatment-emergent ADA
- Number (%) of participants with treatment-boosted ADA
- The summary statistics (including number, median, Q1, Q3, minimum and maximum) of the peak post-baseline titer for participants with treatment-boosted ADA
- The summary statistics (including number, mean, SD, median, Q1, Q3, minimum and maximum) of the ratio of peak post-baseline titer to baseline titer for participants with treatment-boosted ADA
- Listing of ADA peak titer levels and neutralizing antibody status
- Number (%) of participants with neutralizing antibody status

Kinetics of treatment-emergent ADA response

Number (%) of participants with treatment-emergent ADA positive response at each visit will be summarized by each intervention group.

Plot of percentage of participants with treatment-emergent ADA positive response at each visit will be provided by each intervention group.

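### Persistent ADA requires positives strictly more than 84 days apart, but samples are scheduled exactly 84 days apart, so participants with two adjacent positives are classed by visit date or not at all

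*SAP*

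**What the plan says.** SAP 4.8.2 divides treatment-emergent ADA responses into three classes.

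- Persistent: "two or more consecutive ADA positive sampling time points, separated by greater than" a "12-week period (84 days), with no ADA negative samples in between". The strict inequality is given both in words and as a symbol.
- Indeterminate: "defined as a treatment-emergent response with only the last collected sample positive in the ADA assay".
- Transient, the remainder: "defined as a treatment-emergent response that is not considered persistent OR indeterminate".

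The same section says that ADA status "at Visit 2 (Day 1), Week 12, Week 24/EOT and follow up at Week 36 will be provided", which gives three scheduled post-dose samples. SAP 5.4, Table 11, sets the target days: "Visit 3 (Week 12) 85", "Visit 4 (Week 24) 169" and "Visit 5 (Week 36) 253". The protocol's schedule of activities (Section 1.3) allows ±3 days at Weeks 12 and 24 and ±7 days at Week 36.

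Two things are left unsaid. The SAP does not state whether separation is counted on actual sampling dates or nominal visit days. Nor does it state whether separation is measured between neighbouring positives or from the first to the last positive in a run.

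**The concern.** The threshold equals the planned spacing and the inequality is strict. A participant whose two positive samples are both taken on the target day fails the rule by zero days. One taken a day late or early can fall on either side.

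The residual class makes this worse for one pattern. A participant positive only at Week 36 is indeterminate, because nothing later shows whether the response lasted. A participant positive at Weeks 24 and 36 has more evidence of a lasting response. If the gap is 84 days or less, that participant is neither persistent nor indeterminate, and so becomes transient with no negative sample after the response began.

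The same happens at the primary database lock (SAP 4.9), which comes when all participants have finished the 24-week treatment phase. Participants without a Week 36 sample by then have only the Week 12 and Week 24 pair. If both are positive, visit dates settle the class.

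At stake are the persistent and transient counts and their peak-titre summaries, and any exploratory association in SAP 4.8.2.1 that uses persistence.

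**Working it through.** **Inputs.** Target days 85, 169 and 253 (SAP Table 11). Windows ±3, ±3 and ±7 days (Protocol 1.3). Threshold: gap > 84 days (SAP 4.8.2). How visits spread inside the windows is not given, so independent uniform days are an assumption, with a triangular spread as a check.

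**Step 1: the plan's own figure.** 12 × 7 = 84 days.

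**Step 2: planned gaps.** 169 − 85 = 84; 253 − 169 = 84; 253 − 85 = 168. On nominal days neither adjacent gap exceeds 84.

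**Step 3: range of in-window gaps.**

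- Weeks 12 to 24: 84 ± (3 + 3) = 78 to 90 days.
- Weeks 24 to 36: 84 ± (3 + 7) = 74 to 94 days.
- Weeks 12 to 36: 168 ± (3 + 7) = 158 to 178 days.

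**Step 4: share of adjacent gaps above 84 days, uniform visits.** The gap exceeds 84 when the second visit deviates from its target by more than the first does. By symmetry the count is (all combinations − ties) / 2.

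- Weeks 12 and 24: 7 × 7 = 49 combinations, 7 ties; (49 − 7)/2 = 21; 21/49 = 42.9%.
- Weeks 24 and 36: 7 × 15 = 105 combinations, 7 ties; (105 − 7)/2 = 49; 49/105 = 46.7%.

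**Step 5: triangular spread, peaked on the target day.** 41.4% and 44.7%. The result depends little on the shape, provided it is symmetric about the target.

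**Step 6: class by result pattern.**

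| Weeks 12 / 24 / 36 | Nominal days | Actual days, in window |
|---|---|---|
| + + − | transient | persistent in about 43%, otherwise transient |
| + + not available | transient | persistent in about 43%, otherwise transient |
| − + + | transient, no later negative | persistent in about 47%, otherwise transient |
| + + +, first to last | persistent (168 > 84) | always persistent (158 to 178) |
| + + +, neighbours only | not persistent (84 and 84) | at least one gap > 84 in 73.3% (uniform) |
| + − −, − + −, + − + | transient | transient |
| − − + | indeterminate | indeterminate |

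**Step 7: would ≥ be enough?** On actual days, adding the ties gives (21 + 7)/49 = 57.1% and (49 + 7)/105 = 53.3%. Visit date would still decide the class.

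**Step 8: a threshold clear of the windows.** The smallest in-window adjacent gaps are 78 and 74 days. A cut-off of at least 74 days (84 less the largest combined window, 3 + 7 = 10) admits every in-window adjacent pair.

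**The case against.** The strict inequality appears twice, so it may be deliberate. On nominal days with first-to-last separation, the rule simply means three positives in a row. That is demanding but deterministic, and visit-day variation plays no part. This stands in part: variation matters only if actual dates are used. But the SAP does not say which applies, and on nominal days the Weeks 24 and 36 responder is still always transient with no negative afterwards.

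The impact is also narrow, and this stands in full. A reader might infer that the secondary immunogenicity endpoint is at risk. It is not: that endpoint is the incidence of treatment-emergent ADA, which needs one post-dose positive with a negative or missing baseline. A reader might also infer that the efficacy and safety analyses by ADA status rest on persistence. SAP 4.8.2.1 defines ADA positive as treatment-emergent or treatment-boosted. Persistence appears only among example variables for associations that may be explored, and no ADA item is in the testing hierarchy (SAP 4.6).

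The percentages rest on an assumed spread of visits. They are shares of one pattern, not of participants. The documents give no ADA rate, and with about 39 participants on dupilumab the number with exactly two adjacent positives is unknown. Nor should the complement of the percentages, 53% to 57%, be read as an error rate. That would presuppose that two positives 12 weeks apart are truly persistent, and for the + + − pattern a negative does follow.

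**Conclusion.** The point holds for participants with exactly two adjacent positive samples: Weeks 12 and 24 only, including when Week 36 is not yet available at the primary lock, or Weeks 24 and 36 only. On nominal days none of them can be persistent. On actual days about 43% or 47% are (41% and 45% with a triangular spread), assuming independent, in-window visits. The clearest fault is the Weeks 24 and 36 pattern, which becomes transient without a later negative.

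A reader might infer that no participant can ever be persistent. The documents support that only if nominal days and neighbour-to-neighbour separation are both intended, and they specify neither. Measured first to last, three positives in a row are persistent whatever the visit days.

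The effect is confined to descriptive subclasses and optional explorations. It merits correction because those counts and titre summaries will be reported and the change is small. No confirmatory result depends on it.

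**What to change.** In SAP 4.8.2, define a persistent response as ADA positive at two or more consecutive post-dose samples with no negative in between, with the first and last positive at least 74 days apart on actual sampling dates. State that separation is measured from the first to the last positive of the run.

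This makes every in-window adjacent pair persistent. The minimum gap also stops closely spaced samples from counting as persistent by themselves, such as an early end-of-treatment visit soon after Week 12 (Protocol 7.1.1) or an event-triggered sample (Protocol 1.3, footnote n).

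The cost is a short wording change, with no new samples or visits. The downside is that all in-window participants with two adjacent positives become persistent, up from about 43% to 47% of them on actual days. The persistent count may therefore rise noticeably and be less comparable with any programme results that used the strict rule. If that comparison matters, the strict version can be tabulated alongside, with its day-counting convention stated.
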